## **Protocol Synopsis**

**Title:** A Multicenter Double-Blind, Randomized Controlled Study of Etanercept and Methotrexate in Combination or as Monotherapy in Subjects With Psoriatic Arthritis

**Study Phase:** Phase 3

**Indication:** Psoriatic Arthritis (PsA)

---

**Primary Objective:** To evaluate the efficacy of etanercept plus methotrexate therapy and etanercept monotherapy compared to methotrexate monotherapy, in subjects with PsA as measured by the proportion of subjects achieving an American College of Rheumatology (ACR) 20 response at week 24.

**Key Secondary Objective:** To evaluate the efficacy of etanercept plus methotrexate therapy and etanercept monotherapy compared to methotrexate monotherapy as measured by the proportion of subjects achieving Minimal Disease Activity (MDA) at week 24.

**Other Secondary Objectives:**

To evaluate the efficacy of etanercept plus methotrexate therapy and etanercept monotherapy compared to methotrexate monotherapy on the following:

- Other measures of arthritis activity
- Measures of non-arthritic PsA disease activity
- Key patient reported outcomes (PRO) related to physical function and quality of life

**Safety Objectives:**

- To evaluate the safety of etanercept and methotrexate

**Hypotheses:** Primary: Etanercept plus methotrexate therapy and etanercept monotherapy are more efficacious than methotrexate monotherapy as measured by the proportion of subjects with PsA achieving ACR 20 response at week 24.

Secondary: Etanercept plus methotrexate therapy and etanercept monotherapy are more efficacious than methotrexate as measured by the proportion of subjects with PsA achieving MDA response at week 24.

**Primary Endpoint:** ACR 20 response at week 24

**Key Secondary Endpoint:** MDA response at week 24

**Other Secondary Endpoints:**

- Modified Nail Psoriasis Severity Index (modified NAPS) score and change from baseline at week 24
- Leeds dactylitis score and change from baseline at week 24
- Spondyloarthritis Research Consortium of Canada (SPARCC) enthesitis score and change from baseline at week 24
- ACR 20 response at all other measured timepoints
- MDA response at all other measured timepoints
- Psoriatic Arthritis Disease Activity Score (PASDAS) at all measured timepoints
- ACR 50, ACR 70, and components of ACR at all measured timepoints
- Simplified Disease Activity Index (SDAI) and change from baseline at all measured timepoints
- Clinical Disease Activity Index (CDAI) and change from baseline at all measured timepoints
- Disease activity score (28 joint) using the C-reactive protein formula (DAS28-CRP) and change from baseline at all measured timepoints

- Disability Index of the Health Assessment Questionnaire (HAQ-DI) score and change from baseline at week 24
- Medical Outcomes Short Form-36 Questionnaire (SF-36) score and change from baseline at week 24

For subjects with involved body surface area (BSA)  $\geq$  3% at baseline:

- Static Physician Global Assessment of Psoriasis (sPGA) at week 24
- BSA at week 24

**Safety Endpoints:**

- Adverse events
- Serious adverse events
- Laboratory parameters and vital signs

**Study Design:** This is a multicenter, randomized, double-blind controlled study in subjects with PsA. The study will consist of a 30-day screening period, a 48-week double-blind treatment period and a 30-day safety follow-up period. Approximately 840 subjects will be randomly assigned in a 1:1:1 ratio to one of three treatment groups (280 per group): etanercept 50 mg weekly by subcutaneous injection plus oral methotrexate 20 mg weekly, etanercept 50 mg weekly by subcutaneous injection plus oral placebo for methotrexate, and oral methotrexate 20 mg weekly plus placebo for etanercept. Starting at week 24 visit, subjects who have an inadequate response will be provided rescue treatment of etanercept plus methotrexate for the remainder of the study. Original treatment assignments will remain blinded until all subjects reach the week 48 or early termination visit, whichever comes first.

**Sample Size:** Approximately 840 subjects will be enrolled

**Summary of Subject Eligibility Criteria:** Subjects must be adults with active PsA based on the Classification Criteria for Psoriatic Arthritis (CASPAR) who are naïve to etanercept and other biologics and have no prior use of methotrexate for the treatment of PsA. Prior treatment with methotrexate is allowed if indicated for psoriasis as long as discontinuation was not due to toxicity or intolerance and treatment was discontinued  $\geq$  6 months prior to baseline. For a full list of eligibility criteria, please refer to [Section 4.1.1](#) through [Section 4.1.2](#).

**Investigational Product**

**Amgen Investigational Product Dosage and Administration:** Etanercept dosing in the planned study follows the recommended label dosing for subjects with PsA. Etanercept will be provided as a 50 mg pre-filled syringe or matching placebo for injection once weekly for 48 weeks. See [Sections 6.2.1](#).

**Non-Amgen Investigational Product Dosage and Administration:** Methotrexate dosing will begin at a dose of 10 mg on day 1 and will be titrated up to 20 mg weekly over a 4-week period. Methotrexate will be supplied as 2.5 mg capsules or as matching placebo capsules and will be taken once weekly by oral administration for 48 weeks. For those subjects receiving rescue therapy, methotrexate will be dispensed as 2.5 mg tablets. See [Section 6.2.2](#).

**Non-investigational Product**

**Non-Amgen Non-investigational Product Dosage and Administration:** Folic acid dosing will be 5 to 7 mg per week as 1 mg daily per investigator judgment OR administration according to the local standard of care. See [Section 6.3.1](#).

**Procedures:** Written informed consent must be obtained from all subjects before any screening procedures are performed. The following procedures will occur per the Schedule of Assessments: medical and medication history, physical examination, physical measures, vital signs, adverse event and concomitant medication assessment, tuberculosis testing, pregnancy testing, urinalysis, and blood draw for serum chemistry, hematology, hepatitis B and C testing,

C-reactive protein and biomarkers, tender and swollen joint assessment and count, physician global assessment, Leeds dactylitis index, SPARCC enthesitis index, modified NAPS1, BSA, sPGA, radiographs and PROs. For a full list of study procedures, including the timing of each procedure, please refer to [Section 7](#) and the Schedule of Assessments ([Table 1](#)).

**Statistical Considerations:** The primary analysis will occur after all data through week 48 is finalized. The primary analysis of the primary and key secondary endpoints will be based on the full analysis set. Treatment effect between etanercept plus methotrexate therapy and methotrexate monotherapy and between etanercept monotherapy and methotrexate monotherapy will be tested in a Bonferroni-based gatekeeping chain procedure to control the family-wise 2-sided type one error rate at 0.05. Between treatment comparisons will be made using the stratified Cochran-Mantel-Haenszel (CMH) test with baseline body mass index and prior non-biologic disease modifying antirheumatic drug (DMARD) use as the stratification factors. All other efficacy endpoints will be tested at a significance level of 0.05 without adjusting for multiplicity. Safety endpoints will be summarized descriptively based on the safety analysis set. For a full description of statistical analysis methods, please refer to [Section 10](#).

[figure not shown]
---

**Sponsor:** Amgen Inc

Data Element Standards  
Version(s)/Date(s):

Version 4.0 31 October 2013

### Study Design and Treatment Schema

## Study Glossary

Abbreviation or Term	Definition/Explanation
eSAE contingency form	electronic serious adverse event contingency form
ACR	American College of Rheumatology
ALT	Alanine aminotransferase
ALP	Alkaline phosphatase
AST	Aspartate aminotransferase
BMI	Body mass index
BSA	Body Surface Area
CASPAR	Classification Criteria for Psoriatic Arthritis
CDAI	Clinical disease activity index
CMH	Cochran-Mantel-Haenszel
eCRF	Electronic case report form
CRP	C-reactive protein
DAS28-CRP	Disease activity score (28 joint) using the C-reactive protein formula
DILI	Drug-induced liver injury
DMARD	Disease modifying antirheumatic drug
DNA	Deoxyribonucleic acid
EDC	Electronic data capture
Electronic Source Data (eSource)	Source data captured initially into a permanent electronic record used for the reconstruction and evaluation of a trial.
End of Follow-up	Defined as when the last subject completes the last protocol-specified assessment in the study
EOS	End of study for individual subject defined as the last day that protocol-specified procedures are conducted for an individual subject
End of Study (end of trial)	The time when the last subject is assessed or receives an intervention for evaluation in the study.
End of Treatment (EOT)	Defined as the last assessment for the protocol-specified treatment phase of the study for an individual subject
ET	Early termination
FDA	Food and Drug Administration
GCP	Good clinical practice
GRAPPA	Group for Research and Assessment of Psoriasis and Psoriatic Arthritis
HAQ-DI	Disability Index of the Health Assessment Questionnaire
HBV	Hepatitis B virus
HCP	Health care provider
ICH	International Conference on Harmonisation

Abbreviation or Term	Definition/Explanation
Interactive Voice Response System (IXRS)	Telecommunication technology that is linked to a central computer in real time as an interface to collect and process information.
IPIM	Investigational product instruction manual
IRB/IEC	Institutional Review Board/Independent Ethics Committee
MIPA study	Methotrexate in Psoriatic Arthritis Study
MDA	Minimal Disease Activity
Modified NAPS I	Modified Nail Psoriasis Severity Index
van der Heijde mTSS	van der Heijde Modified Total Sharp Score
NSAID	Non-steroidal anti-inflammatory drug
PASDAS	Psoriatic Arthritis Disease Activity Score
PCR	Polymerase chain reaction
PFS	Pre-filled syringe
PI	principal investigator
PPD	Purified protein derivative
PRO	Patient reported outcomes
PsA	Psoriatic arthritis
RBC	Red blood cells
SAP	statistical analysis plan
SDAI	Simplified Disease Activity Index
SF-36	Medical Outcomes Short Form-36 Questionnaire
SPARCC	Spondyloarthritis Research Consortium of Canada
sPGA	Static Physician Global Assessment of Psoriasis
Study Day 1	Defined as the first day that protocol-specified investigational product(s)/protocol required therapies is/are administered to the subject
TBL	Total bilirubin
TNF	Tumor necrosis factor
ULN	Upper limit of normal
VAS	Visual analog scale
WBC	White blood cells

---

## 1. OBJECTIVES

### 1.1 Primary

To evaluate the efficacy of etanercept plus methotrexate therapy and etanercept monotherapy compared to methotrexate monotherapy, in subjects with psoriatic arthritis (PsA) as measured by the proportion of subjects achieving an American College of Rheumatology (ACR) 20 response at week 24.

### 1.2 Key Secondary Objective

To evaluate the efficacy of etanercept plus methotrexate therapy and etanercept monotherapy compared to methotrexate monotherapy as measured by the proportion of subjects achieving minimal disease activity (MDA) at week 24.

### 1.3 Other Secondary Objectives

To evaluate the efficacy of etanercept plus methotrexate therapy and etanercept monotherapy compared to methotrexate monotherapy on the following:

- Other measures of arthritis activity
- Measures of non-arthritic PsA disease activity
- Key patient reported outcomes (PRO) related to physical function and quality of life

### 1.4 Safety Objectives

To evaluate the safety of etanercept and methotrexate.

### 1.5 Exploratory Objectives

To evaluate the efficacy of etanercept plus methotrexate therapy and etanercept monotherapy compared to methotrexate monotherapy on the following:

- Other measures of disease activity including the skin
- Other PROs
- Inhibition of radiographic progression as measured by the van der Heijde modified Total Sharp score (mTSS) for PsA
- To investigate potential biomarkers of disease activity and response to etanercept.
- To investigate the effects of genetic variation in disease genes and drug target genes on PsA and/or subject response to etanercept.

## 2. BACKGROUND AND RATIONALE

### 2.1 Disease

PsA is a chronic inflammatory disorder of the peripheral joints and axial skeleton that occurs in 7% to 34% of patients with psoriasis ([Scarpa et al, 1984](#); [Biondi et al, 1989](#); [Espinoza et al, 1992](#); [Shbeeb et al, 2000](#)), which in turn has a prevalence of 1% to 3% in the general population ([Biondi et al, 1989](#); [Koo, 1996](#)). Articular involvement can vary

widely from an isolated monoarthritis to a very destructive diffuse arthritis mutilans. Other symptoms associated with PsA include dactylitis, enthesitis, and nail changes. Typical nail changes include pitting of the nail, onycholysis, ridges, and thickening of the nail. Although most patients have associated psoriasis, PsA can present without skin changes. Radiographic features include joint erosions, joint space loss, osteolysis that may cause penciling of the phalanx, and periostitis. PsA can lead to permanent destruction of joints and functional disabilities.

## **2.2 Etanercept (Enbrel®) Background**

Tumor Necrosis Factor (TNF) is a naturally occurring cytokine that is involved in normal inflammatory and immune responses. It plays a role in the inflammatory process of plaque psoriasis. Elevated levels of TNF are found in involved tissues and fluids of patients with rheumatoid arthritis, PsA, ankylosing spondylitis, and plaque psoriasis. Two distinct receptors for TNF, a 55 kilodalton protein (p55) and a 75 kilodalton protein (p75), exist naturally as monomeric molecules on cell surfaces and in soluble forms. Biological activity of TNF is dependent upon binding to either cell surface TNF receptor. Etanercept is a dimeric fusion protein consisting of the extracellular ligand-binding portion of the human 75 kilodalton TNF receptor linked to the Fc portion of human IgG1. Etanercept inhibits binding of TNF- $\alpha$  and TNF- $\beta$  (lymphotoxin alpha [LT- $\alpha$ ]) to cell surface TNF receptors, rendering TNF biologically inactive.

In many countries, etanercept is indicated for reducing signs and symptoms, inhibiting the progression of structural damage of active arthritis, and improving physical function in patients with PsA.

Etanercept is also indicated for the treatment of: (1) moderately to severely active rheumatoid arthritis; (2) moderately to severely active polyarticular juvenile idiopathic arthritis in patients aged 2 and older; (3) psoriatic arthritis; (4) active ankylosing spondylitis; and (5) adult patients with chronic moderate to severe plaque psoriasis. Refer to the specific section of the Investigator's Brochure or product label for additional information related to physical, chemical, and pharmaceutical properties and formulations.

## **2.3 Non-Amgen Medicinal Product Background: Methotrexate**

Methotrexate is an antimetabolite used in the treatment of certain neoplastic diseases, psoriasis, and rheumatoid arthritis. Methotrexate or its metabolites inhibit dihydrofolic acid reductase and antagonize thymidylate synthase. Methotrexate is thought to inhibit 5-aminoimidazole 4-carboxamide ribonucleotide transformylase which leads to an

increase in both intracellular and extracellular adenosine. Methotrexate is one of the most commonly used non-biologic disease modifying antirheumatic drug (DMARD) in PsA. Although the use of methotrexate is standard therapy in the medical community and it is mentioned in guidelines in the treatment of PsA, it is not an approved drug for the treatment of PsA in many countries.

Refer to the regional manufacturer package insert for additional information.

## 2.4 Rationale

Etanercept has been approved for PsA by the FDA and Health Canada and is indicated for reducing the signs and symptoms, inhibiting the progression of structural damage of active arthritis, and improving physical function. Etanercept can be used in combination with methotrexate in patients who do not respond adequately to methotrexate alone.

Methotrexate is one of the most commonly used non-biologic DMARD in PsA as monotherapy or in combination therapy with other synthetic DMARDs or with biologic DMARDs. Although methotrexate is commonly used in treating PsA, it is unclear how effective it is in PsA. The most recent randomized placebo-controlled trial of methotrexate in PsA is the Methotrexate in Psoriatic Arthritis (MIPA) study ([Kingsley et al, 2012](#)). This was a 6-month, double-blind, parallel-group study in methotrexate naïve subjects randomized to receive methotrexate (15 mg/wk; n = 109) or placebo (n = 112). In an intent-to-treat analysis, there were no statistically significant improvements in measures of disease activity across groups at 24 weeks. The odds ratios (95% CI) for Psoriatic Arthritis Response Criteria, ACR 20, and Disease activity score (28 joint) responders for the methotrexate and placebo groups were 1.77 (0.97, 3.23; p = 0.06), 2.00 (0.65, 6.22; p = 0.23), and 1.70 (0.90, 3.17; p = 0.10), respectively. In a completer analysis, percent responders for methotrexate and placebo were 34% and 21% for ACR 20 respectively for a difference of 13%. In the PsA pivotal trial, ACR 20 response at week 24 was 50% and 14% in the etanercept and placebo groups respectively for a difference of 36%. Nevertheless, comparisons with the MIPA trial need to be qualified by the fact that the subjects in the etanercept pivotal trial were not uniformly methotrexate naïve. Furthermore, in the MIPA trial the target dose of methotrexate was 15 mg QW, a less than maximal clinically used dose level.

In rheumatoid arthritis, combining TNF inhibitors such as etanercept with methotrexate leads to superior efficacy relative to each agent used alone ([Klareskog et al, 2004](#)). The role of methotrexate in combination with etanercept in PsA remains unclear. Analysis of

data from 440 PsA patients in the Norwegian DMARD longitudinal observational study showed no consistent differences in response over a 12-month period between patients who started their TNF inhibitor as monotherapy or in combination with methotrexate (Fagerli et al, 2014). Similar findings were found in a United States registry (Mease et al, 2013). No difference was found in reaching clinical disease activity index (CDAI) low disease activity or staying in low disease activity on anti-TNF monotherapy vs. combination with methotrexate in this study (Mease et al, 2013). These data suggest key differences in the response of PsA patients compared to RA patients to methotrexate and highlight the importance of characterizing the role of etanercept as a monotherapy agent in PsA.

A new disease activity state called MDA, has been developed and validated (Coates et al, 2010a and Coates et al, 2010b). MDA represents a low disease activity state and would further the 'treat-to-target' approach in PsA. The MDA criteria is specific for PsA and incorporates measures of joint and enthesal inflammation, skin disease, PROs and functional disability to assess the subject's disease activity. The results of the validation analysis support the prognostic value of the PsA MDA criteria and show that subjects achieving MDA are more likely to have a better radiologic outcome (Antoni et al, 2005a, Antoni et al, 2005b).

This study will also aim to characterize the response rates of etanercept on enthesitis, dactylitis, and psoriatic nail changes. The PRESTA trial, assessed two different regimens of etanercept (50 mg twice weekly or 50 mg once weekly) in subjects with psoriasis and PsA. Etanercept 50 mg once weekly resulted in a 70.0% and 81.3% improvement from baseline in enthesitis at week 12 and 24 respectively. Similarly, improvement in dactylitis from baseline at weeks 12 and 24 were 78.4% and 84.8%, respectively (Sterry et al, 2010). There is a paucity of data regarding the efficacy of methotrexate monotherapy on dactylitis and enthesitis in patients with PsA. A recent study looking at the effect of etanercept on the Nail Psoriasis Severity Index (NAPSI) score at week 12 and 24 improved by 50% and 72%, respectively on a weekly dose of Enbrel of 50 mgs (Ortonne et al, 2013). In another recent study comparing improvement in nail changes on methotrexate monotherapy compared to cyclosporine monotherapy, methotrexate demonstrated a 30% improvement at 12 weeks and a 54% improvement at 24 weeks in the NAPSI score (Gümüşel et al, 2011).

## 2.5 Clinical Hypotheses

Primary: Etanercept plus methotrexate therapy and etanercept monotherapy are more efficacious than methotrexate monotherapy as measured by the proportion of subjects with PsA achieving ACR 20 response at week 24.

Secondary: Etanercept plus methotrexate therapy and etanercept monotherapy are more efficacious than methotrexate as measured by the proportion of subjects PsA achieving MDA response at week 24.

## 3. EXPERIMENTAL PLAN

### 3.1 Study Design

This is a phase 3, multicenter, randomized, double-blind controlled study in subjects with active PsA naïve to biologics and with no prior use of methotrexate for the treatment of PsA. The study will consist of a 30-day screening period, a 48-week randomized double-blind treatment period, and a 30-day safety follow-up period.

Approximately 840 subjects will be randomly assigned in a 1:1:1 ratio to one of three treatment groups (280 per arm):

- Etanercept 50 mg weekly by subcutaneous injection plus oral methotrexate 20 mg weekly
- Etanercept 50 mg weekly by subcutaneous injection plus oral placebo for methotrexate
- Oral methotrexate 20 mg weekly plus placebo for etanercept

The overall study design is described by a [study schema](#) at the end of the protocol synopsis section.

The study endpoints are defined in [Section 10.1.1](#).

#### 3.1.1 Rescue Therapy

At or after week 24, subjects who have an inadequate response as defined in Section 3.1.2. will receive rescue therapy with etanercept plus methotrexate until the end of the treatment period. Prior to initiation of etanercept plus methotrexate rescue therapy subjects must complete the procedures outlined for the disease assessment visit as described in [Section 7.2.5](#) and [Table 1](#).

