## **6. TREATMENT PROCEDURES**

### **6.1 Classification of Products and/or Medical Device(s)**

The Amgen Investigational Product used in this study includes: etanercept or placebo for etanercept.

The non-Amgen Investigational product used in this study includes: methotrexate or placebo for methotrexate.

The non-Amgen non-investigational product used in this study includes: folic acid.

The IPIM, a document external to this protocol, contains detailed information regarding the storage, preparation, and administration of etanercept, methotrexate, and folic acid.

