### **6.2.2 Non-Amgen Investigational Product: Methotrexate**

Non-Amgen investigational product methotrexate will also be used in this study. Methotrexate will be distributed using Amgen clinical trial drug distribution procedures. Methotrexate will be supplied as 2.5 mg methotrexate capsules or as matching placebo capsules. For those subjects receiving rescue therapy, methotrexate will be dispensed as 2.5 mg tablets.

Additional details regarding the product(s) are provided in the IPIM.

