### Male Subjects

Male subjects who have had a vasectomy and received medical assessment of surgical success or whose female partner has had a bilateral tubal occlusion are not required to use additional forms of contraception.

Otherwise, male subjects with a partner of child-bearing potential must agree to practice true sexual abstinence (refrain from heterosexual intercourse) or use a condom with spermicide (if spermicide is commercially available) during treatment and for an additional 6 months after the last dose of protocol required therapies. The reliability of sexual abstinence must be evaluated by the investigator and be the preferred and usual lifestyle of the subject.

The female partner should also consider using an acceptable method of effective contraction such as: hormonal, intrauterine device, intrauterine hormonal-releasing system, female barrier method (diaphragm, cervical cap, contraceptive sponge; a female condom is not an option because there is a risk of tearing when both partners use a condom).

Male subjects with a pregnant partner must practice sexual abstinence or wear a condom to prevent exposure of the unborn child to methotrexate through semen.

Unacceptable methods of birth control for male and female subjects include birth control methods that are considered unacceptable in clinical trials and include: periodic abstinence (calendar, symptothermal, postovulation methods), withdrawal (coitus interruptus), spermicides only, and lactational amenorrhoea method.

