### **7.1 Schedule of Assessments**

**Table 1. Schedule of Assessments**

Weeks	30-day Screening	Treatment Period								Disease Assessment (DA)		30-day Follow-Up Safety (EOS) 
		0 (day 1)	4	8	12	16	24	36	48/ET	DA Visit e	DA Follow-up e	
GENERAL & SAFETY ASSESSMENTS												
Informed consent	X											
Randomization via IXRS		X										
Medical/Medication history	X											
Concomitant medications		X	X	X	X	X	X	X	X	X	X	
Adverse events		X	X	X	X	X	X	X	X	X	X	
Serious adverse events	X	X	X	X	X	X	X	X	X	X	X	X
Physical examination a	X	X			X		X	X	X	X	X	
Vital signs	X	X	X	X	X	X	X	X	X	X	X	
Weight	X	X							X	X	X	
Height	X											
LABORATORY ASSESSMENTS												
Pregnancy test (serum) b	X											
Pregnancy test (urine) b,c		X			X		X	X	X			
Tuberculosis testing d	X											
Hematology and chemistry profile	X		X	X	X		X	X	X	X	X	
Hepatitis B surface antigen & core antibody; Hepatitis C virus antibody f	X											
High Sensitivity C-reactive Protein		X	X	X	X	X	X	X	X	X	X	
Urinalysis	X								X			
Biomarker blood sample		X		X			X		X			
INVESTIGATIONAL PRODUCT DISPENSING												
Etanercept/placebo for etanercept dispensation		X	X	X	X		X	X		X g	X	
Methotrexate/placebo for methotrexate dispensation		X	X	X	X		X	X		X g	X	
Folic Acid h		X			X		X	X				
SUBJECT DIARY DISPENSING												
Dispense subject diary		X	X	X	X	X	X	X				
Review subject diary			X	X	X	X	X	X	X	X	X	
DISEASE ASSESSMENTS												
Swollen and Tender joint count	X	X	X	X	X	X	X	X	X	X	X	
Physician Global Assessment of Disease Activity (VAS 0 to 100)		X	X	X	X	X	X	X	X	X	X	
Leeds Dactylitis Index		X	X		X		X	X	X	X	X	
Spondyloarthritis Research Consortium of Canada (SPARCC) Enthesitis Index		X	X		X		X	X	X	X	X	
Modified Nail Psoriasis Severity Index (NAPSI)		X	X		X		X	X	X			
Static Physician Global Assessment of Psoriasis		X	X		X		X	X	X	X	X	
Body Surface Area		X	X		X		X	X	X	X	X	
Radiographs (hands, feet)		X					X		X			

Footnotes defined on next page

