#### **7.4.2 Urine Pregnancy Test**

Urine pregnancy tests will be performed locally at each site. The central laboratory will provide the urine pregnancy tests on visits where required. Urine pregnancy tests must be given prior to dispensing investigational product. If a urine pregnancy test is positive, investigational product must be held; if pregnancy is confirmed, then investigational product must be discontinued.

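### No urine pregnancy test is marked at the separate disease assessment visit where rescue methotrexate can be started

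*Protocol*

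**What the plan says.** Protocol Section 3.1.1 sets the condition for rescue: "Prior to initiation of etanercept plus methotrexate rescue therapy subjects must complete the procedures outlined for the disease assessment visit". It points to Section 7.2.5 and Table 1 for those procedures. Section 7.2.5 lets the visit take place at any time from week 24, and subjects who meet the inadequate response criterion then start etanercept plus methotrexate, titrated up to 20 mg weekly.

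In Table 1 the row "Methotrexate/placebo for methotrexate dispensation" is marked in the DA visit column. The urine pregnancy row is blank there. Footnote c leaves additional pregnancy testing to the investigator.

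Section 7.4.2 says: "Urine pregnancy tests must be given prior to dispensing investigational product". The sentence before it reads: "The central laboratory will provide the urine pregnancy tests on visits where required".

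Methotrexate falls under that rule. Section 6.1 says: "The non-Amgen Investigational product used in this study includes: methotrexate or placebo for methotrexate". Section 6.2.2 describes the rescue supply under the same product: "For those subjects receiving rescue therapy, methotrexate will be dispensed as 2.5 mg tablets".

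**The concern.** The column that sites must complete before rescue leaves out a test that Section 7.4.2, read at face value, requires. For two of the three arms rescue brings no new exposure to methotrexate. For the etanercept monotherapy arm it brings the first methotrexate of the study. (Some of these women may have taken it earlier for psoriasis, which inclusion criterion 107 allows.)

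The protocol itself treats fetal exposure as a hazard. Section 6.9 asks men with a pregnant partner to abstain or use a condom "to prevent exposure of the unborn child to methotrexate through semen", and it stops a woman's therapy as soon as pregnancy is suspected. Before the first dose of study treatment, inclusion criterion 113 requires a negative serum test within 4 weeks and a negative urine test on day 1. A woman who starts methotrexate at an off-schedule rescue visit has no comparable check. What is at stake is subject safety, not an endpoint or an error rate.

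**Working it through.** No sample size, power or alpha figure bears on this point. The check compares rows of Table 1 and then counts days.

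**Columns of Table 1.** Both rows have 12 cells (screening, weeks 0, 4, 8, 12, 16, 24, 36, 48/ET, DA visit, DA follow-up, safety follow-up), so they align. The hematology and chemistry row is marked in both DA columns, so the blanks in the urine row are not a shifted column.

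- Methotrexate or placebo dispensed: weeks 0, 4, 8, 12, 24, 36, DA visit, DA follow-up = 8 columns.
- Urine test marked: weeks 0, 12, 24, 36, 48/ET.
- Dispensed with a test: weeks 0, 12, 24, 36 = 4 of 8.
- Dispensed without a test: weeks 4 and 8, DA visit, DA follow-up = 4 of 8.
- Serum test: screening only.

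Of the four columns without a test, only the DA visit is one at which a woman on etanercept monotherapy can start methotrexate.

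**The two readings of Section 7.4.2.**

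- *Literal:* every dispensing of investigational product needs a test first. Table 1 then conflicts with the text in all four columns, including the one that starts rescue.
- *Narrow:* the sentence only fixes the order of events at visits where Table 1 marks a test. There is then no conflict, but nothing requires a test at a separate DA visit.

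**Age of the last scheduled test.** Target days follow the rule in SAP Appendix A, week × 7 + 1:

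- week 24: 24 × 7 + 1 = 169
- week 36: 36 × 7 + 1 = 253
- week 48: 48 × 7 + 1 = 337

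| Separate DA visit | Latest day | Age of last test |
|---|---|---|
| Between weeks 24 and 36 | 252 | 252 − 169 = 83 days (11.9 weeks) |
| After week 36, follow-up 4 weeks later and by day 337 | 337 − 28 = 309 | 309 − 253 = 56 days (8 weeks) |
| After week 36, follow-up 5 weeks later and by day 337 | 337 − 35 = 302 | 302 − 253 = 49 days (7 weeks) |
| After week 36, no cut-off | 336 | 336 − 253 = 83 days |

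The last row is included because the protocol states no latest day for rescue. The ±7-day visit window in Section 7.2.4 can stretch the gap between the week 24 and week 36 tests from 84 days to 84 + 14 = 98 days.

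**The case against.** The strongest reply is that Section 7.4.2 has been over-read. It comes straight after a sentence about supplying kits where they are required, so it most naturally orders events at a test visit and leaves Table 1 to say which visits those are. Reading it literally would also make weeks 4 and 8 errors. That is a fair reading. It removes the contradiction, but it leaves the methotrexate start at a separate DA visit without a required test.

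A second reply is that the protocol already accepts 84 days between tests for women taking methotrexate weekly. That is true of continuing treatment. Those women began after a negative day 1 test, whereas the DA visit can be a starting point.

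A third is that by week 24 a woman has been under mandatory contraception or abstinence and has had scheduled tests at weeks 0, 12 and 24. This lowers the risk and supports the view that few would be affected.

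A fourth concerns footnote c. The SAP calls rescue open-label, so the site knows that every rescued woman will take active methotrexate and can choose to test her. The original arm stays blinded, so the site cannot tell which woman is new to methotrexate, but it does not need to know that in order to test all of them. What remains is that the test is optional.

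A fifth is that 83 days is an edge case. Day 252 lies inside the week 36 window, which opens on day 246. The last day outside it is day 245, giving 245 − 169 = 76 days. However, the week 36 visit can also run late and a separate DA visit can precede it, so 83 days is a fair nominal figure.

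Finally, the investigational product manual or laboratory manuals may require a test at rescue. They are not among the documents. If they do, Table 1 should show it, because Section 3.1.1 sends sites there.

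**Conclusion.** The point holds and should be corrected. Table 1 marks no pregnancy test in the column that must be completed before rescue, although methotrexate is dispensed in that column. On the literal reading of Section 7.4.2 the protocol contradicts itself. On the narrow reading it lets a woman from the etanercept monotherapy arm start on-study methotrexate on a test up to 83 nominal days old between weeks 24 and 36. After week 36 the figure is 49 to 56 days if the follow-up must fall by day 337, and up to 83 days if no limit applies.

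The gap is limited to women who need testing, in one of three arms, rescued outside the scheduled week 24 and 36 visits. Their number cannot be derived from the documents and is probably small. The efficacy analysis is unaffected. The conclusion assumes that no manual outside the documents already requires the test.

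**What to change.** 1. In Table 1, mark the urine pregnancy test in the DA visit column for all women covered by footnote b. It should apply to all of them because the original arm is blinded.
2. Require a negative result before rescue methotrexate is dispensed.
3. Reword Section 7.4.2 so that the test precedes dispensing at visits where Table 1 marks a test and whenever rescue is started. This also settles weeks 4, 8 and the DA follow-up without adding tests there.

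The cost is one mark in the table, the accompanying wording in Section 7.4.2 and a few extra kits of a type the central laboratory already supplies. The added site burden is minor, since the DA visit already includes a blood draw and a physical examination.
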